1. INTRODUCTION

This document describes the statistical methods and data presentations to be used in the summary and analysis of safety and efficacy data from Protocol GBI 04-01. Background information is provided for the overall study design and objectives. The reader is referred to the study protocol and case report forms (CRFs) for details of study conduct and data collection.

2. STUDY OBJECTIVE(S), TREATMENTS, AND ENDPOINT(S)

2.1 Study Objectives

The objective of this study is to determine the immunologic and overall safety associated with long-term use of Alphanate® in individuals diagnosed with severe hemophilia A (Factor VIII:C less than 0.01 IU/mL), who have been previously treated with plasma-derived Factor VIII products other than Alphanate® and who have no history of developing either antibody inhibitors to Factor VIII or nonspecific inhibitors of coagulation.

2.2 Treatment Comparisons

Alphanate® is the only study treatment being administered, so this is an open label, non-comparator study.

2.3 Study Endpoints

2.3.1 Efficacy

There are two secondary efficacy endpoints in this study:

- The amount of product used per year as part of at-home prophylaxis and therapy for bleeding episodes, and
- A physician's qualitative assessment of hemostasis (evaluated as "None", "Moderate", "Good", or "Excellent" in response to therapy with Alphanate® received by the subject in a hospital or another location under the physician's direct supervision.

2.3.2 Safety

Safety will be evaluated on the basis of numerous assessments. The primary safety assessment will be made on the presence/absence of the development of Factor VIII inhibitors.

Additional secondary safety assessments will be made on:

- The frequency, nature, causality and severity of adverse events,
- The occurrence of changes in biochemical parameters which would indicate renal or hepatic impairment,
- The incidence of seroconversion to human immunodeficiency virus type 1 and 2 (HIV-1/HIV-2), hepatitis A virus (HAV), hepatitis B virus (HBV), hepatitis C virus (HCV) or parvovirus B19 in subjects seronegative for these viruses at the time of enrollment.

CONFIDENTIAL

3. STUDY DESIGN

3.1 Overall Study Design

This is a phase IV, non-randomized, multi-center study to assess the safety of Alphanate® as the sole source of Factor VIII concentrate for prophylaxis and treatment of all bleeding episodes and surgical procedures for a period of at least two years and a minimum of 50 exposure days, or, if 50 exposure days are not reached, for a maximum of 30 months.

3.2 Overall Schedule of Time and Events

CONFIDENTIAL

Test	Screening ¹	Enrollment ²	Seven to 14 days Post Infusion 1	In Hospital and In Clinic Treatments	Every Three Months until Month 30 and/or Off-Study ³	Unshed
Sign Informed Consent Form	X					
Physical Examination medical & past treatment history, vital signs, height & weight	X					
Abbreviated Physical Exam interim medical history, vital signs, & weight		X			X	X
Hematology Panel CBC with WBC differential and platelet count	X				X	X
Biochemistry Panel ALT, AST, AP, LDH, BUN, total bilirubin, and creatinine	X				X	X
Viral Serology HBsAg, and antibodies to HAV, HBcAb, HBsAb, HCV, HIV1/HIV-2, and parvovirus	X	X ²			X	X ⁵
Parvovirus B19 PCR Assay performed only if seronegative for parvo B19 at enrollment			X			
CD4 Count	X					
Factor VIII:C	X	X ²			X	X
Factor VIII:C Inhibitor (two sets of samples)	X	X ²			X ⁴	X ^{6,7}
Collect 2 mL citrated plasma for inhibitor testing			X			
Plasma for inhibitor characterization performed only if subject develops an inhibitor					X ⁸	
Serum for storage Draw approx 5 mL of serum and aliquot into three vials of at least 1.5 mL of sample each. Freeze and retain the sample at	X	X			X	X
Patient Diary if the Alphanate® is to be self-administered			X	X	X	X
Physician's Assessment of Hemostasis evaluated as "None," "Moderate," "Good," or "Excellent"				X		

1. Perform at least 72 hours after the most recent administration of any F VIII conc. or any other blood products.
2. These tests are to be performed at enrollment (baseline testing) only if the subject received any Factor VIII, cryoprecipitate, or whole product treatment *after* screening tests were performed.
3. Quarterly testing will be \pm 10 days of scheduled testing date. Schedule the visit at least three days after an infusion with Alphanate®.
4. If subject develops an inhibitor, repeat assay at two week intervals until either the inhibitor falls to < 0.6 BU/mL or it is clear that the inhibitor titer will not fall.
5. Perform only if subject exhibits clinical or subjective symptoms indicating possible viral infection.
6. Perform only if a) there is a clinical indication that the normal dosage of Alphanate® is not providing adequate hemostasis or b) surgery.
7. If an inhibitor titer is detected at a titer of greater than or equal to 10 BU/mL, collect a 10 mL sample of citrated plasma. For an inhibitor titer less than 10 BU/mL, collect a 50 mL sample of citrated plasma. If a 50 mL is required, this sample can be obtained in multiple draws within a two-week period.

CONFIDENTIAL

4. SAMPLE SIZE CONSIDERATIONS

Assuming a maximum biannual rate of inhibitor incidence of three percent in multi-transfused hemophilia patients, the 95% one-sided confidence interval for this incidence rate in a sample of 50 subjects is up to two percent. Thus, with a sample of 50 evaluable subjects monitored for two years, if one subject develops an antibody inhibitor to Factor VIII with a titer higher than 0.6 modified BU/mL, that persists for at least one month, the incidence of inhibitors to Factor VIII will be judged to be higher than that for patients with hemophilia A who are treated with currently marketed Factor VIII concentrates. If the sample size is increased to 80 subjects, no more than 1 subject may develop an antibody inhibitor to Factor VIII.

5. ANALYSIS POPULATIONS

5.1 Safety Population

The safety analysis population consists of all patients who were randomized and received at least one Alphanate® treatment; no treated patients will be excluded from the safety analysis population.

6. CONSIDERATIONS FOR DATA ANALYSIS

6.1 Programming Environment

All analyses will be conducted using SAS® version 9.2.

6.2 Strata and Covariates

There are no planned strata or covariate adjustments planned for in the analysis.

6.3 Subgroups

There are no planned subgroup analyses.

6.4 Multiple Comparisons and Multiplicity

There are no planned adjustments for multiplicity, especially since the analysis is primarily descriptive.

6.5 Significance Level

Unless otherwise noted, all statistical analyses will be conducted with a significance level (α) of 0.05 and utilize two-sided testing.

6.6 Statistical Notation and Methodology

Unless stated otherwise, the term “descriptive statistics” refers to the number of subjects (n), mean, median, standard deviation (SD), minimum, and maximum for continuous data and frequencies and percentages for categorical data. Unless otherwise noted, all data collected during the study will be

CONFIDENTIAL

included in data listings and will be sorted first by subject number and then by date within each subject number.

7. DATA HANDLING METHODS

7.1 Missing Data

Every effort will be made to obtain required data at each scheduled evaluation from all patients who have been enrolled. There will be no imputation for missing data.

7.2 Visit Windows

Study periods will be windowed as follows:

- Post-Infusion # 1 – 7 to 14 days after infusion
- Quarterly Visits - ± 10 days

7.3 Data Derivations

Baseline values will be considered as the last non-missing assessment prior to first dose of study drug.

On-treatment will be considered as all days between the first dose of study drug and until 1 day post Off-Study.

8. STUDY POPULATION

8.1 Subject Disposition

Subject disposition will be presented for all subjects. Subjects who completed and discontinued from the study will be summarized with descriptive statistics. Reasons for early discontinuation also will be presented with frequencies and percentages for all categories.

8.2 Protocol Deviations

Protocol deviations will be presented in a data listing and include date of violation and description of the event.

8.3 Demographic Characteristics

Demographic and baseline characteristic data will be summarized with descriptive statistics for age and race.

CONFIDENTIAL

8.4 Medical History

Medical history will be presented in a data listing and include body system, diagnosis and the onset month and year as appropriate.

8.5 Concomitant Medications

Concomitant medications will be summarized with descriptive statistics by drug using the WHO Drug dictionary. Data listings will display all data by preferred term and verbatim name. Prior medications will be excluded from the summary but be included in the listing.

9. STATISTICAL ANALYSIS

9.1 Primary Analysis

Analysis of the primary safety endpoint will be conducted on the Safety Population. The primary safety endpoint, presence/absence of Factor VIII inhibitors, will be summarized with frequencies and percentages.

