7.4 Every 3 Months until Month 30 and/or Off-Study

Samples for quarterly testing will be drawn \pm **10 days** of the scheduled visit date. At each of these visits, the following procedures will be performed:

1. Abbreviated physical examination including: interim medical history, vital signs (pulse, respiratory rate, oral temperature, blood pressure) and weight;
2. Factor VIII coagulant activity (Factor VIII:C);
3. Factor VIII inhibitor levels (BU/mL) in two sets of samples;
4. Hematologic status will be assessed by: complete blood count (CBC) with white blood cell (WBC) differential and platelet count.
5. Serum chemistry tests including: alanine aminotransferase (ALT), aspartic aminotransferase (AST), alkaline phosphatase (AP), lactic acid dehydrogenase (LDH), blood urea nitrogen (BUN), creatinine and total bilirubin;
6. Viral and serological tests including: testing for HBsAg, and for antibodies to HAV, HBcAb, HBsAb, HCV, HIV-1/HIV-2 (only if seronegative at baseline) and parvovirus B19 by routine immunoassay (only in subjects who are seronegative at baseline);
7. A sample of venous blood will be drawn from which approximately 5 mL of serum will be prepared and aliquoted into three vials of at least 1.5 mL of sample each. The samples will be frozen and retained at -20°C in the event that they are required for later serological or virology tests.

If at any quarterly visit, **the subject tests positive for the presence of Factor VIII inhibitors (inhibitor titer of greater than 0.6 modified BU/mL), based upon the value determined by the central reference laboratory**, the procedures specified in section 7.12 (Subjects Who Develop Inhibitors) will also be performed.

Contains Confidential and Proprietary Information of Grifols Inc.

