7.8 Miscellaneous

All enrollment tests should be performed prior to the first administration of Alphanate®. Samples drawn for quarterly testing will be drawn \pm 10 days of the scheduled visit date. The presence of inhibitors will be determined by the Nijmegen modification of the Bethesda assay (see below); the Factor VIII source for this assay will be normal pooled plasma. **Inhibitor titers will be considered valid if the subject's Factor VIII level is at or below baseline (less than 0.01 IU/mL)**, therefore, the subject should be scheduled for the quarterly visit at least three days after an infusion with Alphanate®.

If the subject's Factor VIII levels are higher than baseline at the time the plasma sample is drawn, then the subject will be rescheduled for testing within one week of the notification of the invalid result.

Assays for inhibitor to Factor VIII will be performed locally (i.e., at the coagulation testing laboratory for each clinical site) to support decisions regarding treatment. Duplicate plasma samples will be collected at each time point for confirmatory testing at a central reference laboratory. The central laboratory will utilize the Nijmegen modification of the Bethesda assay to improve reliability.¹⁷ The modification involves the following changes in reagents: (1) buffering of the normal pooled plasma used in the assay and control with 0.1 M imidazole to pH 7.4 and (2) replacing the imidazole buffer in the control mixture with immunodepleted Factor VIII-deficient plasma. In addition, to further improve the accuracy of the assays, a standardized immunodepleted plasma will be used for the performance of the assay at all clinical sites, as well as at the central reference laboratory.

The local laboratories will not be required to test for Factor VIII inhibitors using the Nijmegen modification of the Bethesda assay, but are required to provide the sponsor with a detailed description of the procedure used.

Contains Confidential and Proprietary Information of Grifols Inc.

Only the results of the assays from the central reference laboratory will be used in the determination and analysis of the primary endpoint for the clinical trial.

To determine the risk of transmission of parvovirus B19, subjects who are seronegative at enrollment will be tested approximately one week after receiving the first infusion with Alphanate[®] for the presence of parvovirus B19 by Polymerase Chain Reaction (PCR) testing.

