7.11 Subjects Who Develop Inhibitors

If at any quarterly visit, the subject tests positive for the presence of Factor VIII inhibitors, (inhibitor titer of 0.6 modified BU/mL or greater) based on the local lab test and confirmed by the central reference laboratory test result, the following steps should be taken:

- For an inhibitor titer of greater than or equal to 10 BU/mL,
 - Collect a 10 mL sample of citrated plasma and send to the central reference laboratory.
 - Withdraw the subject only after performing all required testing (see Section 7.4) and only after receiving confirmation of the inhibitor titer from the central reference laboratory.
- For an inhibitor titer less than 10 BU/mL,

Contains Confidential and Proprietary Information of Grifols Inc.

- Collect a 50 mL sample of citrated plasma. This sample can be obtained in multiple draws within a two-week period and sent to the central reference laboratory.
- Repeat inhibitor titer assay at two-week intervals until:
 1. the inhibitor titer decreases to < 0.6 modified BU/mL or
 2. the subject's participation in the study is ended or
 3. it becomes apparent that, after repeated assays at two-week intervals, the inhibitor titer will not decrease during the course of the study (the investigator should first consult with the Project Manager prior to making this determination).
 - If the subject's inhibitor level is less than 5 BU/mL and treatment with Alphanate® at higher doses remains effective in achieving hemostasis, then the subject will continue the current treatment regimen and testing will be performed as described in Section 7.4 above.
 - If Alphanate® treatment either becomes ineffective in achieving hemostasis, even if the inhibitor titer remains below 5 BU/mL, or if the inhibitor level rises to greater than or equal to 5 BU/mL, as confirmed by test results from the central reference laboratory, then the subject will be withdrawn from the study.

Subjects withdrawn from the study may either be treated with alternate concentrates or commence a treatment program with Alphanate® for the induction of immune tolerance. The treating physician, in consultation with Grifols Office of Medical Affairs, will determine the alternate treatment or product and the immune tolerance protocol.

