8.1 Primary Endpoint

Incidence of antibody inhibitors to Factor VIII in at least 50 evaluable subjects will be determined following a period of at least two years and a minimum of 50 exposure days or if 50 exposure days are not reached, a maximum of 30 months. Only one exposure-day will be accrued for each surgical episode independent of the number of days of treatment or the number of infusions. For the purpose of this endpoint only, a subject is determined to be evaluable when his clinical experience after the date of enrollment includes at least 50 CEDs of treatment with Alphanate[®] or when he develops inhibitors with a titer greater than or equal to 5 BU/mL as determined by the central reference laboratory.

Contains Confidential and Proprietary Information of Grifols Inc.

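### SAP 9.1 counts an undefined presence of inhibitor in all treated subjects, and neither applies nor cites the plan's own rule for the primary endpoint

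*SAP*

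**What the plan says.** - **SAP 9.1** places the primary analysis in the Safety Population and says "The primary safety endpoint, presence/absence of Factor VIII inhibitors, will be summarized with frequencies and percentages". It gives no titer, persistence requirement, laboratory, evaluability condition or decision rule, and does not refer to SAP 4.
- **SAP 5.1** defines the only analysis population: "The safety analysis population consists of all patients who were randomized and received at least one" infusion. It adds that no treated patient is left out. The study is not randomized.
- **SAP 4 and protocol 9.2.1** give the same rule. The event is an inhibitor "with a titer higher than 0.6 modified BU/mL, that persists for at least one month". One event in 50 evaluable subjects means that incidence is called higher than with marketed concentrates; with 80 subjects, one event is tolerated. Both state that, under an assumed maximum rate of three percent, "the 95% one-sided confidence interval for this incidence rate in a sample of 50 subjects is up to two percent".
- **Protocol 8.1** defines evaluability: "For the purpose of this endpoint only, a subject is determined to be evaluable when his clinical experience" meets one of two conditions, namely at least 50 cumulative exposure days (CEDs) on the product or a central-laboratory titer of at least 5 BU/mL.
- **Protocol 7.8**: "Only the results of the assays from the central reference laboratory will be used in the determination and analysis of the primary endpoint". It also makes a titer valid only when Factor VIII is at or below baseline.
- **Positivity** is worded in two ways. Protocol 7.4 (and 7.5) uses "inhibitor titer of greater than 0.6 modified BU/mL" on the central value; protocol 7.11 uses "inhibitor titer of 0.6 modified BU/mL or greater) based on the local lab test and confirmed by the central reference laboratory".

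**The concern.** A programmer working from SAP 9.1 has no instruction to require persistence, to restrict the denominator, or to reach the verdict that SAP 4 describes. Nothing else in the SAP fills the gap. SAP 2.3.2 repeats the presence/absence wording, SAP 1 points to the protocol only for conduct and data collection, and the title of planned Table 12.13 refers to positive tests, not cases.

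Because the rule turns on a single subject in 50, classifying one subject differently reverses the conclusion about the product. A bare percentage would also hide how little 50 subjects can say about a 3% reference rate.

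**Working it through.** **1. The plan's own figure.** Inputs from SAP 4: n = 50 or 80, one-sided 95%. Exact (Clopper-Pearson) upper limit = 0.95 quantile of Beta(x+1, n−x).

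- 0/50: 1 − 0.05^(1/50) = 5.8%
- 1/50: 9.1%
- 0/80: 3.7%
- 1/80: 5.8%

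A Wilson limit gives 5.1% for 0/50 and 8.5% for 1/50. A Wald limit around 3% gives 0.03 + 1.645 × √(0.03 × 0.97/50) = 7.0%. None of these is two percent; only the point estimate 1/50 = 2.0% matches. None of the four exact limits lies below 3%.

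**2. How often the count rule flags a product at the reference rate.** I read the plan's biannual rate as a rate per two years, because follow-up is two years. At p = 0.03:

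- n = 50, at least 1 event: 1 − 0.97^50 = 1 − 0.218 = 78%
- n = 80, at least 2 events: 1 − 0.97^80 − 80 × 0.03 × 0.97^79 = 1 − 0.087 − 0.216 = 70%

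**3. Event definition.** Take 50 subjects who all reach 50 CEDs, one with a single positive central titer that is gone within a month, and no other positives. SAP 4 counts 0/50 and the product passes. SAP 9.1 can be read as 1/50 = 2.0%.

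**4. Denominator.** Illustration with assumed counts: 60 treated, 50 reach 50 CEDs, and one of the other 10 has a persistent inhibitor of 2 BU/mL.

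- Safety Population: 1/60 = 1.7% (upper limit 7.7%)
- Protocol 8.1 as written: 0/50 = 0% (5.8%)
- Protocol 8.1 plus anyone who meets the SAP 4 event: 1/51 = 2.0% (9.0%)

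The middle line is a gap in protocol 8.1 itself. A persistent titer above 0.6 but below 5 BU/mL with fewer than 50 CEDs is an event under SAP 4, yet the subject is not evaluable. The all-treated set keeps him.

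**5. Persistence that cannot be seen.** Protocol 7.14 discontinues subjects with a titer of 5 BU/mL or more, or a lower titer with ineffective treatment. Protocol 7.11 stops the two-week repeats when participation ends. Such a subject may leave before one month of persistence is documented, and no counting rule covers him.

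**6. Dropout.** The documents give no rate, so I assumed 10%, 20% and 30% over two years. With constant hazards, λ = −ln(0.97)/2 and μ = −ln(1−d)/2 per year, events observed by time t are E(t) = λ/(λ+μ) × [1 − e^(−(λ+μ)t)]. For a true 3%:

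- Safety rate E(2): 2.85%, 2.69%, 2.53%
- Evaluable rate (with all events kept) if 50 CEDs are reached at time T: E(2) / [E(T) + e^(−(λ+μ)T)]. For T = 100 days: 2.89%, 2.77%, 2.65%. For T = two years: 3.16%, 3.35%, 3.59%.

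The evaluable rate crosses 3% when T is about one year.

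**The case against.** The strongest defence is that the rule exists in SAP 4, that SAP 6.4 calls the analysis primarily descriptive, and that all treated subjects are a reasonable set for a safety endpoint. The last point stands: the Safety analysis should stay, and the word 'randomized' in SAP 5.1 has no numerical effect because no treated patient is excluded. But SAP 4 is a sample-size section that 9.1 never invokes, and it uses 'evaluable' without defining it.

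Four stronger readings are tempting and are not supported:

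- *A local-only positive would count.* Protocol 7.8 still restricts the primary endpoint to central results, and nothing in SAP 9.1 displaces it. What is missing is a cross-reference.
- *Central positives will miss the repeat tests that show persistence.* Protocol 7.4 and 7.5 start the inhibitor procedures on the central value alone, and footnote 4 of the schedule orders two-week repeats with no local-test condition. The difficulty is confined to the entry wording of 7.11.
- *Dropout biases the two populations in opposite directions.* That holds only if 50 CEDs take about a year or more. On the daily or every-other-day prophylaxis described in protocol 7.9.2, they would take roughly 50 to 100 days, and both rates then fall below 3%.
- *The SAP dropped a promised confidence limit.* Neither document promises a limit on the observed rate; reporting one is my recommendation.

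**Conclusion.** The point holds as an inconsistency within the plan. SAP 9.1 does not carry the event definition, the evaluable denominator or the laboratory source that the plan sets elsewhere for the same endpoint, and the SAP defines no evaluable set. The event definition matters most: one reclassified subject is 2 percentage points in 50 and reverses the verdict. In the assumed dropout scenarios the denominator moves the rate by no more than 0.59 points.

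Separately, the two percent limit in SAP 4 and protocol 9.2.1 is wrong. Even 0/50 leaves an upper limit of 5.8%, so a clean result would not exclude 3%, while the count rule would flag a product truly at 3% in 78% (n = 50) or 70% (n = 80) of trials. These two probabilities rest on reading the rate as per two years. The 60-subject example and the dropout figures rest on assumed inputs and serve only to show direction and size.

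**What to change.** 1. **SAP 5.1.** Replace 'randomized' with 'enrolled' (wording only). Add an Evaluable Population: treated subjects with at least 50 CEDs, or a central titer of at least 5 BU/mL, or who meet the SAP 4 event definition. Align protocol 8.1.
2. **SAP 9.1.** Cite SAP 4 and protocol 7.8. Define the event as a titer above 0.6 modified BU/mL persisting at least one month on valid central results. For counting only, show the result with and without subjects discontinued for a centrally confirmed inhibitor before persistence could be observed, and keep them in the denominator both ways.
3. **Reporting.** Give count, percentage and exact one-sided 95% upper limit in the Evaluable and Safety Populations, with the number of subjects who have no valid post-baseline central result. Make no general statement about the direction of dropout bias.
4. **SAP 4 and protocol 9.2.1.** Correct the stated limit, and give the rule's 78% and 70% probabilities of flagging at 3%.
5. **Protocol 7.4, 7.5 and 7.11.** Reconcile the two thresholds and the two laboratory conditions. Correct the pointer in 7.4 and 7.5 to section 7.12, which covers other blood products; the inhibitor procedures are in 7.11.

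A rate per patient-year, and treating the count as an alert instead of a verdict, are optional.

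Cost: SAP wording, a few table rows, and a protocol correction (8.1, 9.2.1, 7.4, 7.5, 7.11) that needs IRB review under protocol 13.1. The central titers and infusion dates are already collected. The limits will look less favourable than a bare percentage.

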A study of the incidence of inhibitors in previously-treated patients (PTPs) carried out by McMillan *et al.* included 1306 hemophilia patients whose mean age was 18, and who were followed for up to four years. Thirty-one of these individuals (2.4 percent) developed inhibitors to Factor VIII; of these, 29 had been diagnosed with severe hemophilia A. The incidence of new inhibitors was eight per 1,000 patient-years of observation.

In a study of PTPs treated with recombinant Factor VIII (Kogenate®), by Schwartz *et al.*, inhibitor formation was observed in only 1 of 86 (1.2%) patients following repeated exposure to the product.¹⁶ The mean annual per capita consumption of Factor VIII in this subgroup was estimated to be approximately 78,000 units annually.

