9.2 Planned Method of Analysis

9.2.1 Primary Endpoint

Incidence of Antibody Inhibitors to Factor VIII in Individuals Treated with Alphanate[®]

Assuming a maximum biannual rate of inhibitor incidence of three percent in multi-transfused hemophilia patients, the 95% one-sided confidence interval for this incidence rate in a sample of 50 subjects is up to two percent. Thus,

Contains Confidential and Proprietary Information of Grifols Inc.

with a sample of 50 evaluable subjects monitored for two years, if one subject develops an antibody inhibitor to Factor VIII with a titer higher than 0.6 modified BU/mL, that persists for at least one month, the incidence of inhibitors to Factor VIII will be judged to be higher than that for patients with hemophilia A who are treated with currently marketed Factor VIII concentrates. If the sample size is increased to 80 subjects, no more than 1 subject may develop an antibody inhibitor to Factor VIII.

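### The primary inhibitor result is a crude percentage with no interval, although time at risk varies and the yardstick is a two-year rate; a time-at-risk estimate should stand beside it.

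*SAP*

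**What the plan says.** SAP 9.1 contains the whole primary analysis. "Analysis of the primary safety endpoint will be conducted on the Safety Population", and the endpoint, "presence/absence of Factor VIII inhibitors, will be summarized with frequencies and percentages". SAP 5.1 admits anyone who "received at least one Alphanate® treatment; no treated patients will be excluded from the safety analysis population", so there is no minimum time at risk.

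Planned follow-up in SAP 3.1 is "for a period of at least two years and a minimum of 50 exposure days". The same sentence caps the stay of subjects with less exposure than this at month 30. Protocol 7.14 lists several routes to early exit, including withdrawal by the subject's own choice.

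The yardstick is tied to time. SAP 4 begins "Assuming a maximum biannual rate of inhibitor incidence of three percent in multi-transfused hemophilia patients" and then sets a rule for 50 evaluable subjects followed for two years. One inhibitor above 0.6 modified BU/mL that lasts a month or more means that the incidence is judged higher than with marketed concentrates. With 80 subjects, one such case is tolerated. Protocol 9.2.1 has the same text.

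SAP 7.1 says that missing data are not imputed and gives no censoring rule. No display listed in SAP 11.1 is described as time-to-event, per patient-year or two-year.

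**The concern.** A crude percentage treats a subject who leaves after one infusion as a full non-event. It also counts an inhibitor found in months 24 to 30 against a rate framed on two years. The first pulls the figure down and the second pushes it up. Two trials of the same product could therefore report different incidences only because their follow-up differed, and a reader who sets the figure against 3% could not tell.

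The protocol's Introduction shows how far the two measures can part. One cohort of previously treated patients is reported as 31 of 1,306 (2.4%) over up to four years, and also as a rate: "The incidence of new inhibitors was eight per 1,000 patient-years of observation". At constant hazard that rate is 1 − exp(−0.016) = 1.6% over two years, so the crude percentage is about 1.5 times the two-year figure.

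With no interval specified, a result of no events would appear as a bare 0%, whatever the amount of follow-up behind it.

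**Working it through.** **The plan's own figure.** SAP 4 and protocol 9.2.1 say that the one-sided 95% interval for a 3% rate in 50 subjects reaches two percent. This does not reproduce. The normal approximation gives 0.03 + 1.645 × √(0.03 × 0.97 / 50) = 7.0%. The exact one-sided upper limit is 5.8% for 0/50 and 9.1% for 1/50. Only the point estimate 1/50 equals 2%. That is a separate defect, and nothing below relies on it.

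**Inputs.**
- Two-year risk of 3% (SAP 4), taking *biannual* to mean per two years.
- Follow-up of 24 months, or up to 30 (SAP 3.1).
- Entry to the denominator after one treatment (SAP 5.1).
- Assumed, because the documents do not give them: the share leaving early, when they leave, the share staying to month 30, and a constant hazard.

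**Hazard.** h = −ln(0.97)/2 = 0.01523 per year.

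**Expected crude percentage when the true two-year risk is 3.00%.**
- All followed for 24 months: 3.00%.
- All followed for 30 months: 1 − exp(−2.5h) = 3.74%.
- 20% stay to month 30, no dropout: 0.8 × 3.00 + 0.2 × 3.74 = 3.15%.
- Leavers spread evenly over 0 to 24 months have a mean risk of 1 − 0.03/(2h) = 1.51%. With 20% leaving and completers stopping at month 24: 0.2 × 1.51 + 0.8 × 3.00 = 2.70%. With 30% leaving: 2.55%.
- 20% leave straight after one infusion, the rest stop at month 24: 0.8 × 3.00 = 2.40%.

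**Sensitivity to the hazard.** If all the risk falls evenly in the first six months, evenly spread leavers carry 87.5% of the full risk. The crude figure is then 0.2 × 2.625 + 0.8 × 3.00 = 2.92% with 20% leaving and 2.89% with 30%. Staying to month 30 adds nothing.

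**Size against sampling error, n = 50.** Crude risks of 2.70%, 3.00% and 3.74% mean 1.35, 1.50 and 1.87 expected events. The chance of at least one event, 1 − (1 − p)^50, is 75%, 78% and 85%.

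**What person-time adds.** The two-year equivalent of x events in PY person-years is 1 − exp(−2x/PY). The one-sided 95% exact Poisson upper limit replaces x by 2.996 for no events and by 4.744 for one event.

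| Person-years in 50 subjects | 1 event: crude | 1 event: two-year equivalent (upper limit) | 0 events: two-year upper limit |
|---|---|---|---|
| 50 | 2.0% | 3.9% (17.3%) | 11.3% |
| 75 | 2.0% | 2.6% (11.9%) | 7.7% |
| 100 | 2.0% | 2.0% (9.1%) | 5.8% |
| 125 | 2.0% | 1.6% (7.3%) | 4.7% |

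Here 100 person-years is 50 subjects for two years and 125 is 50 subjects for 30 months. The 50 person-year row is an extreme case.

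**The word biannual.** Read as twice a year, 3% would be 1 − 0.97⁴ = 11.5% over two years. The next sentence of the plan speaks of two years of monitoring, which supports the two-year reading.

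**The case against.** The strongest objection is that the rule is a count: one case in 50, or no more than one in 80. SAP 9.1 reports frequencies, so it comes close to giving that numerator. This stands. A reader might infer that the reported figure is unrelated to what is judged, but the documents do not support that. The count can still include a case after month 24.

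Second, early leavers are in the denominator only because the SAP uses all treated subjects. Under the evaluability definition in protocol 8.1, most of them would drop out of it. This is largely right, so the dropout figures overlap with the population question. Evaluability would not settle the timing, though, because it rests on 50 exposure days or a titer of at least 5 BU/mL and not on two years. Every-other-day infusion, which protocol 7.9.2 mentions, reaches 50 exposure days in about 100 days.

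Third, 3.74% is a ceiling. If subjects with 50 exposure days stop at month 24, it requires that nobody reaches 50 by then. A reader might set 3.74% against 2.55% and infer a distortion of about 1.4 to 1.5 times. That pairs two extremes built on assumed dropout, and the documents support no such figure.

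Fourth, 8 per 1,000 patient-years might be taken for a second benchmark. It is background from a cited study, and neither SAP 4 nor protocol 9.2.1 uses it.

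Fifth, SAP 9.3.1 and 9.3.2 and the inhibitor tables and listings in SAP 11.1 would let a reader recover event times and exposure. SAP 6.4 also calls the analysis mainly descriptive. Both are true, but neither supplies a prespecified estimate, censoring rule or limit.

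**Conclusion.** The point holds in a limited form. SAP 9.1 gives a crude percentage with no limit, time at risk varies by design and by early exit, and the comparison is framed on two years. For a true two-year risk of 3% and constant hazard, plausible departures run from about 2.4% to 3.15%, with a ceiling of 3.74%. A front-loaded hazard brings the dropout cases back to about 2.9%. All of these rest on assumed exit and extension shares and on the two-year reading of *biannual*.

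The effect is modest beside the imprecision of 50 subjects: the exact one-sided upper limit for one case in 50 is 9.1%. With no events, both approaches estimate 0%, and only the upper limit shows how much follow-up lies behind it.

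A reader might conclude that a Kaplan-Meier estimate should replace the primary summary. The documents do not compel that. About one or two events are expected at the 3% rate. Kaplan-Meier also needs non-informative censoring, while protocol 7.14 allows discontinuation for an inhibitor below 5 BU/mL that makes treatment ineffective, possibly before persistence is shown. It would also leave the count rule as it is. The mismatches in population and event definition are separate and would remain.

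**What to change.** In SAP 9.1, keep the count and percentage and add:
- the incidence per patient-year, from first infusion to the last valid central-laboratory titer (validity as in protocol 7.8), with an exact Poisson 95% limit. State whether the limit is one- or two-sided, since SAP 4 uses one-sided and SAP 6.5 defaults to two-sided;
- its two-year equivalent, or a 24-month Kaplan-Meier estimate labelled as supportive;
- a separate line for events after month 24.

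Protocol 9.2.1 has "Assuming a maximum biannual rate of inhibitor incidence of three percent" and SAP 4 has the same phrase. In both, replace the words *biannual rate* with *two-year cumulative incidence*.

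The cost is a few lines of SAP text, the wording change in the protocol and one extra table. Infusion dates (protocol 7.9.1, SAP 9.3.1) and quarterly inhibitor results (protocol 7.4) are already collected.
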